Official Title: Efficacy of Transcutaneous Auricular
Vagus Nerve Stimulation on Alleviating Major
Depressive Disorder in Patients With Acute
Coronary Syndrome After Percutaneous Coronary
Intervention: A Prospective, Double-
Blind, Randomized Controlled Study

NCT Number:

Date: April 30, 2024

1. Introduction

Acute Coronary Syndrome (ACS) is a clinical syndrome spectrum pathologically based on atherosclerotic plaque rupture or erosion, with subsequent complete or incomplete occlusive thrombus formation. It includes unstable angina and acute ST-segment elevation or non-ST-segment elevation myocardial infarction, representing a severe manifestation of coronary artery disease (CAD) and a leading cause of annual cardiovascular morbidity and mortality^[1]. The incidence and mortality rates of ACS are substantial, with nearly half of CAD-related deaths occurring post-ACS, posing a severe threat to patients' quality of life^[2].

Percutaneous coronary intervention (PCI) is a primary treatment for ACS. However, as an invasive procedure, PCI carries inherent procedural risks. Coupled with patients' lack of understanding, excessive concerns about postoperative complications, stent longevity, drug side effects, and treatment costs, patients diagnosed with ACS face a series of negative physical and mental health risks following PCI. A meta-analysis on anxiety and depression in post-PCI patients indicated^[3] that varying degrees of anxiety and depression are prevalent, with rates ranging from 20% to 82%. Furthermore, these mental health issues, prone to occur after PCI, have been confirmed to significantly impact treatment adherence and prognosis^[4]. Depression is estimated to be the second leading cause of global disability^[5], and the mortality risk is substantially increased in patients with depression following an ACS event^[6]. The onset, progression, and outcomes of cardiovascular disease are closely linked to psychological factors, characterizing it as a psychosomatic condition. Ample evidence indicates that psychological factors can promote the development of cardiovascular disease, while anti-anxiety and antidepressant treatments can significantly improve the prognosis of patients with cardiovascular disease^[7].

The incidence of anxiety post-PCI ranges from 25% to 37%^[8], and the prevalence of depression is as high as 20% to 40%. While PCI rapidly and effectively achieves vascular recanalization and reperfusion, the requirement for lifelong medication post-procedure imposes a substantial psychological and economic burden on patients and

society. Gu et al.^[9] conducted Hospital Anxiety and Depression Scale (HADS) questionnaires on 170 patients one day before and one day after PCI. They found that on the day before PCI, 34.7% experienced anxiety and 23.5% experienced depression; whereas on the day after PCI, 54.7% experienced anxiety and 44.7% experienced depression. Concerns regarding surgical complications, quality of care, postoperative decline in cardiac function, and procedural failure contributed to a marked increase in anxiety and depression prevalence post-PCI. Most clinicians focus solely on resolving coronary obstruction, often overlooking patients' emotional disorders. However, patients with anxiety and depression frequently exhibit unhealthy lifestyles and poor medication adherence, leading to unfavorable prognoses. Kala et al.^[10] analyzed the one-year rehospitalization rate and its influencing factors in 145 post-PCI patients, finding that the rate was associated with the presence of depressive symptoms. Li et al.^[8] followed 303 PCI patients for one year to observe the incidence of major adverse cardiovascular events (MACE, e.g., new non-fatal myocardial infarction, stent restenosis, heart failure, arrhythmia, death). They found that the risk of MACE in anxious patients was 3.742 times that of non-anxious patients, and in depressed patients was 3.087 times that of non-depressed patients. Moreover, the risk for patients with both anxiety and depression was 7.303 times that of patients without these conditions, indicating that anxiety and depression are predictors of poor prognosis in CAD patients after stent implantation. Therefore, routine assessment of anxiety and depression in PCI patients and active measures to improve negative emotions are warranted in clinical practice to enhance patient outcomes.

Antidepressant medications are considered first-line treatment for depression. However, studies have found that one-third to one-half of patients do not respond to multiple antidepressants^[11]. A response typically requires at least 4 weeks, and side effects such as nausea, cardiovascular issues, sexual dysfunction, and headaches are common, leading to low medication adherence^[12]. Cognitive Behavioral Therapy (CBT) is a major psychotherapy, but its complexity and cost hinder accessibility for low-income patients with depression^[13]. Thus, despite urgent need, current treatments for major depression remain far from satisfactory.

Vagus Nerve Stimulation (VNS) is an FDA-approved somatic therapy for treatment-resistant depression (TRD) that produces clinically significant antidepressant effects^[14]. However, despite its efficacy, surgical risks, high procedural costs (\$30,000 - \$50,000), and potential side effects limit its appeal and result in low clinical utilization^[15]. To overcome these barriers associated with invasive VNS (iVNS), a non-invasive transcutaneous auricular VNS (taVNS) method has been developed and is garnering increasing attention. Anatomical studies indicate that the ear is the only location on the human body surface with afferent vagus nerve distribution^[16]. According to the "bottom-up" mechanism of the central nervous system, electrical stimulation propagation may follow a reverse pathway from peripheral nerves to the brainstem and central structures^[17]. Therefore, direct stimulation of afferent nerve fibers on the ear should produce effects similar to classical VNS in alleviating depressive symptoms, without the burden of surgical intervention^[18]. The first study on taVNS for depression was conducted in 2009. Since then, a series of clinical studies have demonstrated that taVNS can effectively improve depressive symptoms^[19-21]. However, research on taVNS for treating depression in ACS patients after PCI is limited. We will employ a randomized controlled clinical trial to investigate the antidepressant effect of taVNS in post-PCI patients with moderate or severe depression.

2. Objectives

2.1 Study Aims

Aim 1: To compare the improvement in depression, anxiety, and quality of life between patients receiving transcutaneous auricular vagus nerve stimulation or sham stimulation using a randomized controlled design.

Aim 2: To compare the improvement in multiple physiological indicators between patients receiving transcutaneous auricular vagus nerve stimulation or sham stimulation using a randomized controlled design.

2.2 Study Endpoints (or Evaluation Metrics)

2.2.1 Primary Endpoint (or Primary Evaluation Metric) and Definition

Hamilton Depression Rating Scale (HAMD) score at Week 8: The 17-item HAMD is convenient, has clear criteria, is easy to master, and can be used to assess depressive symptoms in various conditions including depression, bipolar disorder, and neurosis, being particularly suitable for major depressive disorder.

Scoring criteria:

No depressive symptoms: Total score ≤ 7 ; Mild depression: Total score ≥ 8 and ≤ 17 ; Moderate depression: Total score > 17 and ≤ 24 ; Severe depression: Total score > 24 .

2.2.2 Secondary Endpoints (or Secondary Evaluation Metrics) and Definitions

1. Hamilton Anxiety Rating Scale (HAMA) score during follow-up: The total score effectively reflects the severity of anxiety symptoms and can be used to evaluate the severity of anxiety in patients with anxiety and depressive disorders and to assess the effects of various drug and psychological interventions.

According to data from the Chinese Scale Collaboration Group: Total score ≥ 29 : Possible severe anxiety; Total score ≥ 21 : Definite significant anxiety; Total score ≥ 14 : Definite anxiety; Total score > 7 : Possible anxiety; Total score ≤ 7 : No anxiety symptoms.

2. HAMD response rate: Reduction in HAMD-17 score $\geq 50\%$.

3. HAMD remission rate: Post-treatment HAMD-17 score ≤ 7 .

4. Beck Depression Inventory (BDI) score: A tool specifically designed to assess depression severity. The entire questionnaire comprises 21 groups of items, each with 4 statements preceded by corresponding numbers as grade scores.

Scoring criteria: 0-4: (Essentially) no depressive symptoms; 5-7: Mild depression; 8-15: Moderate depression; ≥ 16 : Severe depression.

5. Generalized Anxiety Disorder 7-item (GAD-7) score: The GAD-7 consists of 7 items aiming to understand how often the respondent has been bothered by 7 problems including feeling nervous or anxious over the past 2 weeks.

Scoring rules: Each item scores 0-3, total score 21. 0-4: No generalized anxiety; 5-9: Mild generalized anxiety; 10-14: Moderate generalized anxiety; 15-21: Severe generalized anxiety

6. PTSD Checklist-Civilian Version (PCL-C) score: Developed in 1994 by the Behavioral Science Division of the US National Center for PTSD, translated into Chinese by Professors Jiang Chao and Zhang Jie in 2003. The scale includes 17 items categorized into 3 characteristic symptom clusters: re-experiencing (5 items), avoidance (7 items), and hyperarousal (5 items). Each item uses a Likert 5-point scale from 1 (not at all) to 5 (extremely). Total score range 17-85, with higher scores indicating a higher likelihood of PTSD.

Test results: 17-37: No significant PTSD symptoms; 38-49: Some degree of PTSD symptoms; 50-85: Significant PTSD symptoms, possible PTSD diagnosis

7. Quality of Life Scale (SF-36) score: The 36-Item Short Form Health Survey (SF-36) is widely used, covering 8 domains: physical functioning, role-physical, bodily pain, general health, vitality, social functioning, role-emotional, and mental health. Patients are scored on quality of life to assess changes in physical, energetic, emotional, and mental health, using a percentage system. Higher scores indicate better function and quality of life.

8. Heart Rate Variability (HRV): A 10-minute resting ECG is recorded. HRV analysis methods mainly include time-domain, frequency-domain, and non-linear methods.

Key time-domain parameters include:

SDNN (Standard Deviation of all Normal-to-Normal [NN] intervals): Reflects overall autonomic nervous system activity, primarily sympathetic tone. Normal value (141 ± 39) ms; lower values suggest increased sympathetic activity and reduced adaptability.

- SDANN (Standard Deviation of the Averages of NN intervals in all 5-minute segments): Evaluates sympathetic nervous system activity. Normal value (127 ± 35) ms.

- rMSSD (Root Mean Square of Successive Differences between adjacent NN intervals): Reflects parasympathetic (vagal) activity. Normal value (27 ± 12) ms.

- pNN50 (Percentage of adjacent NN intervals differing by >50 ms): Lower values indicate lower parasympathetic activity.

Frequency-domain indicators include:

- Total Power (TP) (≤ 0.4 Hz): Reflects overall autonomic nervous system activity and regulatory capacity.
 - High Frequency (HF) (0.15–0.40 Hz): A good indicator of parasympathetic (vagal) function, influenced by respiration depth.
 - Low Frequency (LF) (0.04–0.15 Hz): Controlled by both sympathetic and parasympathetic systems; some studies consider it influenced by sympathetic activity, serving as a reliable indicator of cardiac sympathetic activity, affected by baroreflexes.
 - Very Low Frequency (VLF) (0.003–0.040 Hz)
 - Ultra-Low Frequency (ULF) (≤ 0.003 Hz)
 - LF/HF ratio: Reflects the balance of sympathetic-parasympathetic tone.
9. Echocardiography: Includes left ventricular anterior-posterior diameter (diastolic/systolic) and left ventricular ejection fraction (LVEF).
10. Venous blood biomarkers: Levels of N-terminal pro-B-type natriuretic peptide (NT-proBNP), interleukin-1 (IL-1), interleukin-6 (IL-6), tumor necrosis factor-alpha (TNF- α), high-sensitivity C-reactive protein (hs-CRP).
11. Incidence of Major Adverse Cardiovascular Events (MACE): Including death, myocardial infarction, and target vessel revascularization (definitions based on Academic Research Consortium [ARC] criteria).
-

3. Study Design

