6.2 Concomitant Treatment and Follow-up Visits

All enrolled patients will receive standard post-PCI medication and strict secondary prevention for coronary artery disease.

Follow-up visits will occur at 4, 8, 12, and 16 weeks post-randomization. Follow-up content includes: HAMA, HAMD, BDI, GAD-7, PCL-C, and SF-36 scale assessments; HRV measurement; echocardiography; venous blood tests; assessment of smoking/alcohol cessation and lifestyle improvement; record of follow-up visits (time, location, results); presence of angina or heart failure-related symptoms; occurrence of MACE (time, management, outcome); adverse reactions.

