9.3.2 Analysis of Secondary Endpoints

Comparisons of HAMA scores, BDI scores, GAD-7 scores, PCL-C scores, SF-36 scores, HRV parameters, echocardiography parameters, and blood biomarkers between groups will be performed using t-tests or non-parametric tests. Comparison of HAMA response rates, remission rates, and MACE incidence between groups will be performed using chi-square tests.

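### SDANN and ULF are listed as HRV parameters, but the specified 10-minute ECG is too short to estimate either of them meaningfully

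*Protocol*

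**What the plan says.** HRV is item 8 under Protocol section 2.2.2, "Secondary Endpoints (or Secondary Evaluation Metrics) and Definitions". The recording is fixed in one sentence: "A 10-minute resting ECG is recorded". The parameters listed under it include:

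- "SDANN (Standard Deviation of the Averages of NN intervals in all 5-minute segments", with the reference "Normal value (127 ± 35) ms";
- "Ultra-Low Frequency (ULF) (≤ 0.003 Hz", with no reference value;
- SDNN, with the reference "Normal value (141 ± 39) ms";
- total power (TP), defined only by an upper limit of 0.4 Hz, and VLF from 0.003 to 0.040 Hz.

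The section does not say what recording length lies behind its normal values.

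Section 6.2 repeats the measurement at weeks 4, 8, 12 and 16 ("HRV measurement; echocardiography; venous blood tests") and gives no other recording length. Section 9.3.2 compares HRV parameters between groups without exempting any: "SF-36 scores, HRV parameters, echocardiography parameters, and blood biomarkers between groups will be performed using t-tests or non-parametric tests". Table 1 in section 10.1 has fields for both SDANN and ULF. The only 24-hour quantity in the protocol is the average heart rate in the exclusion criteria (section 4.2), which nothing links to HRV or to follow-up.

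**The concern.** The recording length and two of the parameters do not fit together. SDANN describes variation between 5-minute segments and needs many of them. ULF covers periods of 333 s (1/0.003) and longer and needs a record many times that length. A 600-second trace provides neither.

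Aim 2 in section 2.1 is a comparison of physiological indicators. Section 2.2.2 gives SDANN a meaning (sympathetic activity) and a normal value, so readers will interpret the result. A null finding would say almost nothing about slow variability. A nominally significant one could not be attributed to the quantity named. An SAP cannot repair this, because the information is not in the trace.

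**Working it through.** The protocol attaches no sample size or power figure to HRV, so there is no stated figure to reproduce. The counts in steps 1 to 3 use only the protocol's own numbers. The confidence limits and step 4 need assumptions, given where used.

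**Inputs.** Recording 10 min = 600 s; segment 5 min = 300 s; ULF limit 0.003 Hz; normal SDANN 127 ± 35 ms; normal SDNN 141 ± 39 ms (all section 2.2.2); 60 per group (section 9.1); two-sided 0.05 (section 9.4).

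**1. SDANN**
- Segments: 600/300 = 2, so df = 1 and SDANN = |m1 − m2|/√2.
- If segment means are independent and normal (assumption), the 95% limits for the true SD are the estimate times √(df/χ²): √(1/5.024) = 0.45 to √(1/0.000982) = 31.9.
- On the same assumption the sampling coefficient of variation (CV) of one patient's SDANN is √(1 − 0.798²)/0.798 = 76%.
- For comparison, an assumed 24-hour record has 86,400/300 = 288 segments and limits of 0.92 to 1.09.

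**2. The listed normal values**
- SDANN = 127 ms from two segments requires |m1 − m2| = 127 × √2 = 180 ms, for example 767 and 947 ms (about 78 and 63 beats per minute) in adjacent resting periods.
- Two SDs below the normal, 127 − 70 = 57 ms, still requires 57 × √2 = 81 ms.
- 127²/141² = 0.81. If both normals come from the same recordings, roughly 81% of the SDNN variance lies between 5-minute segments. The SDNN normal is therefore open to the same question.

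**3. ULF and neighbouring bands**
- Frequency resolution: 1/600 = 0.00167 Hz. The next frequency, 2/600 = 0.00333 Hz, is already above 0.003 Hz, so one non-zero Fourier frequency lies in the band.
- Cycles seen at the band's upper limit: 600 × 0.003 = 1.8. Slower components cannot be separated from trend.
- One frequency gives about 2 df: CV √(2/2) = 100%, and 95% limits 2/7.378 = 0.27 to 2/0.0506 = 39.5 times the estimate. An assumed 24-hour record would give 259 frequencies.
- The other bands hold 23 (VLF), 66 (LF) and 150 (HF) frequencies. VLF starts at 0.003 Hz, so its lower edge also has only 1.8 cycles. TP has no lower limit and so includes the unresolved ULF part.

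**4. Illustration of lost power for SDANN**
- Assume a between-patient CV of 35/127 = 0.276 and independent normal segment means.
- Total CV: √[(1 + 0.276²)(1 + 0.756²) − 1] = 0.831. Reliability: 0.276²/0.831² = 0.11.
- A true standardized effect of 0.5 shrinks to 0.5 × √0.11 = 0.166. Power at 60 per group: Φ(0.166 × √30 − 1.96) = about 15%.
- With 288 segments the reliability is 0.976 and the power about 77%.

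**The case against.** The best defence is that both parameters can be computed and that imprecision in one patient averages out over a group: a 100% per-recording CV contributes about 100%/√60 = 13% of the mean in a group of 60. That is true for sampling error. Averaging does not turn a two-segment difference, or a single frequency entangled with trend, into the long-period variability that the names denote. The loss of power also remains.

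The illustration in step 4 is open to challenge, since it takes its between-patient CV from the very normal value whose fit is in doubt and assumes independent segments. It shows the direction and rough size of the loss; the finding itself rests on the segment and frequency counts.

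A reader might infer more than the protocol supports:

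- **That the trial would produce false autonomic effects.** Measurement noise in a randomized comparison leaves each test's type I error intact. The cost is power and interpretability.
- **That most patients would be labelled abnormal.** Nothing in the protocol classifies patients against an HRV normal value; section 9.3.2 plans only group comparisons. ULF has no listed normal at all.
- **That the SDANN normal is impossible here.** The arithmetic shows a poor fit. Since the source recording length is not stated, one can say only that it does not appear to apply.

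The 24-hour heart rate in section 4.2 may imply longer monitoring at screening. It does not resolve the mismatch, because it is not linked to HRV or repeated at follow-up, but it does make a longer recording a possible alternative to deletion.

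**Conclusion.** The mismatch stands on the protocol's own figures: two segments and 1 df for SDANN, one non-zero Fourier frequency and at most 1.8 cycles for ULF. Neither can be estimated meaningfully from the specified trace. Their between-group tests would be valid in type I error but very low in power (about 15% against 77% in the SDANN illustration, under its assumptions) and not interpretable as the named quantities.

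The reach is limited. Two sub-parameters of one secondary endpoint are affected directly, with a related caution for TP, the lower edge of VLF and the listed normals. HAMD at Week 8, the sample size, rMSSD, pNN50, LF, HF and LF/HF are untouched. SDNN can still be computed, as variability within the 10 minutes. It should be corrected, but it does not threaten the trial's main conclusion.

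**What to change.** - Remove SDANN and ULF from the 10-minute HRV endpoint in section 2.2.2 and from Table 1 in section 10.1. Alternatively, if a long recording is already made at the relevant visits, say so and derive these two from that recording only.
- Define TP with a lower frequency limit that a 600-second trace can resolve, and state that limit.
- Keep VLF only with a stated caution about its lower edge.
- State the recording length behind each listed normal value. Do not interpret 10-minute results against these values unless they are confirmed for that length.

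Deletion needs only edits to the text and the form. It adds no procedure or patient burden and gives up two parameters that could not have been interpreted. The alternative costs nothing extra only where the long recording already exists.

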3.1 Overall Study Design

An investigator-initiated, single-center, prospective, randomized, double-blind, parallel-group controlled study.

4. Study Population

4.1 Inclusion Criteria

- Age ≥ 18 years;
- Meets diagnostic criteria for ACS;

- 14 days to 12 months post-successful PCI, with stable vital signs;
- Meets Diagnostic and Statistical Manual of Mental Disorders, Fifth Edition (DSM-V) diagnostic criteria for Major Depressive Disorder;
- HAMD-17 score ≥ 7 and < 24 , with HAMA score $<$ HAMD score;
- After full disclosure of condition, the patient or legal representative refuses psychiatric consultation and declines antidepressant medication or psychotherapy;
- Patient or legal representative voluntarily participates in the study and provides written informed consent.

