5.1 Randomization

5.1.1 Method for Generating Random Allocation Sequence

Stratified block randomization will be used: Eligible patients will be randomly assigned to Group A or B in a 1:1 ratio. Using R software, stratification will be based on age (two levels: 18-60 years, >60 years) and gender (two levels: male, female), resulting in 4 strata. Within each stratum, patients will undergo randomization with varying block sizes. The output will determine the stimulation device assigned to each patient.

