6.1 Study Intervention Implementation Steps

1. For outpatients or inpatients who are 2 weeks to 12 months post-ACS PCI, a psychiatrist will conduct assessments using DSM-V, HAMD, and HAMA scales. Patients meeting criteria for mild to moderate depression will be advised to receive appropriate treatment. If they refuse and meet inclusion/exclusion criteria, they will sign informed consent, enroll in the clinical trial, and baseline data will be collected.

2. Device Usage Method

Eligible patients will receive transcutaneous auricular non-invasive vagus nerve stimulation while awake. The electrode and the patient's left ear target area will first be disinfected with 75% alcohol. An abrasive gel will then be applied to the left concha cymba and tragus area for gentle abrasion, wiped off, and the area disinfected again with alcohol. Conductive gel will be applied to the electrode output points. The electrode will be placed on the patient's left ear, ensuring the output points are positioned on the left tragus. Pulses will be delivered via the Xidian Keyue brand (Product No.: BS-TVNS600) vagus nerve stimulator. The stimulation current will be gradually increased to the maximum intensity tolerable by the patient, defined as the threshold intensity.

Active Stimulation Group: Stimulation at threshold intensity, with parameters: pulse frequency 20 Hz, pulse width 250 μ s, pulse current 0.5-3 mA. Stimulation cycle: 30 seconds ON, 30 seconds OFF.

Sham Stimulation Group: Device, parameter adjustment, and placement identical to the active group. The stimulator is programmed to deliver stimulation only for the first 5 seconds of each session, with no subsequent stimulation.

Both groups will undergo electrical stimulation twice daily for 20 minutes each session, for a total treatment duration of 8 weeks.

All patients will be trained on how to turn the stimulator on/off, attach the electrode to the ear and position it, and increase the intensity. All subsequent operations will be performed by the patient at home. Patients can obtain assistance via telephone

or site visits if they have questions. Each patient will be given a diary card to record usage date, duration, adverse reactions, and suggestions. Patients are required to complete daily entries, which will be checked during assessment visits.

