9.3 Efficacy Analysis and Statistical Methods

9.3.1 Analysis of Primary Endpoint

Comparison of HAMD scores between groups will be performed using t-tests or non-parametric tests.

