10.1 Case Report Form / Electronic Data Record

Table 1: Baseline Characteristics

Gender(%)	Male Female	Age ,mean (SD), y	
Marriage status(%)	Single Married	BMI (kg/m ²)	
Residential Area(%)	Urban Rural	Living alone(%)	Yes No
Education(%)	Primary education Secondary School Technical secondary school or higher	Occupation(%)	Retired Unemployed Employed
cigarette(%)	Yes No	Participant consumes alcoholic beverages(%)	Yes No
Type of health insurance(%)	New rural cooperative medical scheme Urban Employee Basic Medical Insurance Uninsured	Previous PCI.or CABG events(%)	Yes No

Previous cardiac events(%)	Yes No	Diagnosticn (%)	NSTEMI UA STEMI
Previous PCI.or CABG events(%)	Yes No	Hypertension(%)	Yes No
Diabetes(%)	Yes No	Yes No	Yes No
hsCRP (mg/L)		Total implanted stents mean (SD), pc	
NYHA_Class(%)	I II	EF (%)	
IL-1 (pg/ml)		IL-6 (pg/ml)	
TNF- α (pg/ml)		LVD (d/s)	
HAMA		HAMD	
BDI		GAD-7	
SF-36		PCL-C	
HbA1c (%)		HRV (SDNN) (ms)	
HRV (SDANN) (ms)		HRV (RMSSD) (ms)	
HRV (TP) (Hz)		HRV (HF) (Hz)	

HRV (LF) (Hz)		HRV (VLF) (Hz)	
HRV (ULF) (Hz)		NT-proBNP (ng/mL)	
hsCRP (mg/L)			

Note: BMI: Body Mass Index; NSTEMI: Non-ST-Elevation Myocardial Infarction; UA: Unstable Angina; STEMI: ST-Elevation Myocardial Infarction; PCI: Percutaneous Coronary Intervention; CABG: Coronary Artery Bypass Grafting; LVEF: Left Ventricular Ejection Fraction; NT-proBNP: N-terminal pro-B-type Natriuretic Peptide; hs-CRP: High-sensitivity C-Reactive Protein; IL-1: Interleukin-1; IL-6: Interleukin-6; TNF- α : Tumor Necrosis Factor-alpha; LVD (d/s): Left Ventricular Diameter (diastolic/systolic); HAMA: Hamilton Anxiety Rating Scale; HAMD: Hamilton Depression Rating Scale; BDI: Beck Depression Inventory; GAD-7: Generalized Anxiety Disorder 7-item; SF-36: 36-Item Short Form Health Survey; PCL-C: PTSD Checklist-Civilian Version; HRV: Heart Rate Variability; HbA1c: Glycated Hemoglobin; SDNN: Standard Deviation of NN intervals; RMSSD: Root Mean Square of Successive Differences; TP: Total Power; HF: High Frequency; LF: Low Frequency; VLF: Very Low Frequency; ULF: Ultra-Low Frequency.*

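### Time since PCI varies from 14 days to 12 months at entry but is neither on the baseline form nor in the analysis, so a cheap gain in precision and interpretability is left unused

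*Protocol*

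**What the plan says.** Protocol section 4.1 sets the entry window: "14 days to 12 months post-successful PCI, with stable vital signs". Section 6.1 restates it: "For outpatients or inpatients who are 2 weeks to 12 months post-ACS PCI". Visits follow at 4, 8, 12 and 16 weeks after randomization (section 6.2), and the primary endpoint is HAMD-17 at Week 8 (section 2.2.1).

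Section 5.1.1 fixes the strata: "stratification will be based on age (two levels: 18-60 years, >60 years) and gender (two levels: male, female), resulting in 4 strata".

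Table 1 in section 10.1 is the baseline form. Its nearest items are ACS type, previous cardiac events, previous PCI or CABG (yes/no) and "Total implanted stents mean (SD), pc". It has no index PCI date and no interval from PCI to randomization. One cell is damaged in the text at hand, but it shows a yes/no item, which could not hold an interval.

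For the primary endpoint, section 9.3.1 states: "Comparison of HAMD scores between groups will be performed using t-tests or non-parametric tests". Section 9.3.2 does the same for the continuous secondary endpoints, including "HRV parameters, echocardiography parameters, and blood biomarkers between groups will be performed using t-tests or non-parametric tests". Neither section, nor the general methods in section 9.4, names a covariate.

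**The concern.** Both aims in section 2.1 are framed as improvement. The second reads: "Aim 2: To compare the improvement in multiple physiological indicators between patients". How much a patient improves without active stimulation may depend on how long ago the PCI was. It is reasonable to expect this of mood, and of ejection fraction, NT-proBNP, inflammatory markers and heart rate variability. If it does, patients in each arm carry different expected changes, and an unadjusted test counts that spread as noise.

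Two things follow. The confidence interval is wider than it need be. And a reader of the baseline table cannot see whether the arms were similar in this respect, or which phase after PCI the result describes. The information is within reach, because the site must establish the PCI date to apply the entry criterion.

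**Working it through.** **Inputs from the protocol.** Window 14 days to 12 months (4.1). Follow-up to 16 weeks (6.2). 56 per group before dropout, 10% dropout, 60 per group enrolled, alpha 0.05, power 0.80 (9.1). Two-sided tests (9.4).

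**Assumed, because the protocol gives no figure.** The share of Week 8 HAMD variance explained by time since PCI (R²): 0.02 to 0.10. The share of patients in an early phase: 20 to 50%. Extra HAMD improvement in early over late patients: 2 to 4 points. HAMD standard deviation: 6.

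**1. Spread of the window.** 365/14 ≈ 26-fold. A patient entered at 2 weeks reaches Week 8 at 2 + 8 = 10 weeks after PCI and ends follow-up at 2 + 16 = 18 weeks. A patient entered at 12 months starts at 52 weeks and reaches Week 8 at 60. Their observation periods do not overlap in time since PCI.

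**2. The plan's own sample size as an anchor.** This point does not rest on the sample size, but a power calculation needs an effect. Reading the stated 57% as a standardized difference of 0.57 gives 2 × (1.96 + 0.842)²/0.57² = 48.3, so 49 per group (50 by the t-test), not 56. That mismatch is a separate matter. I therefore take the effect that 56 per group detects with 80% power, d = 0.534, and use 0.535.

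**3. Power with and without adjustment.** Completers: 60 × 0.90 = 54 per group. Adjustment divides d by √(1 − R²). The equivalent of 56 per group is 56 × (1 − R²).

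| R² (assumed) | effective d | power, 54 per group | equivalent of 56 |
|---|---|---|---|
| 0 (unadjusted) | 0.535 | 78.7% | 56 |
| 0.02 | 0.540 | 79.5% | about 55 |
| 0.05 | 0.549 | 80.7% | about 53 |
| 0.10 | 0.564 | 82.7% | about 50 |

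The gain is about 0.8, 2 and 4 points of power.

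**4. Is that R² range coherent?** With half the patients early and a gap g, the between-phase variance is 0.25 × g²: 1.0 at g = 2 and 4.0 at g = 4. Against a total variance of 36 (SD 6) this is 2.8% and 11.1%. So R² of 2 to 10% corresponds roughly to a gap of 2 to 4 HAMD points.

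**5. Chance imbalance at 60 per group.** The standard error of the difference in early share is √(2p(1 − p)/60).

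| early share p (assumed) | SE | P(difference ≥ 10 points) | P(difference ≥ 15 points) |
|---|---|---|---|
| 20% | 0.073 | 17% | 4% |
| 30% | 0.084 | 23% | 7% |
| 50% | 0.091 | 27% | 10% |

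An imbalance of 10 to 15 points with a gap of 2 to 4 shifts the HAMD contrast by 0.10 × 2 = 0.2 to 0.15 × 4 = 0.6 points. The standard error of that contrast at SD 6 is 6 × √(2/60) ≈ 1.1 points, so the shift stays well inside one standard error.

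**The case against.** The strongest reply is that nothing here is invalid. Allocation is concealed, the sham arm is concurrent, and spontaneous change does not differ systematically between arms. Chance imbalance in any prognostic factor is already part of the standard error and of the 5% alpha. This stands, and it sets the ceiling on the point.

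A reader might go further and infer that the wide window confounds both aims, so that natural recovery could pass for a taVNS effect. The documents do not support that. Their only evidence on the time course is in the Introduction: depression on a symptom questionnaire in 23.5% the day before PCI and 44.7% the day after, in a passage saying that patients' worries "contributed to a marked increase in anxiety and depression prevalence post-PCI". That spans two days around the procedure. It says nothing about diagnosed major depressive disorder from day 14 onward. No passage says that mood or cardiac markers are still moving at 2 weeks or settled by a year, and patients with unstable angina are eligible as well as those with infarction.

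A reader might also infer that an imbalance could never be detected. That is too strong. The PCI date is checked at eligibility and can be recovered from source records at this single centre, and baseline HAMD, ejection fraction and biomarkers on the form might hint at an imbalance. What is true is narrower: the form as written does not capture the interval.

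Finally, covariates are often left to a statistical analysis plan, and one may exist. That is fair for a supportive table. But the protocol itself sets out the baseline form and names specific unadjusted tests, so both are open to comment.

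**Conclusion.** The point holds as a weakness in precision and interpretability. The window is wide, time since PCI is not on the form, and the named analyses cannot use it. Type I error and freedom from systematic bias are not in question.

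The size is modest and rests on assumptions. If time since PCI explains 2 to 10% of Week 8 HAMD variance, adjustment takes power from 78.7% to between 79.5% and 82.7% at 54 completers per group. The anchor is the effect that 56 per group detects at 80% power. With baseline HAMD also in the model, the separate contribution of time since PCI could be smaller where the two overlap. For the cardiac endpoints the protocol offers no basis for a figure, and I give none.

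Label: cheap improvement.

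**What to change.** - **Section 10.1, Table 1:** add the number of days from index PCI to randomization, and report it by arm.
- **Sections 9.3.1 and 9.3.2:** for continuous endpoints, replace the unadjusted comparison with ANCOVA on the baseline value of the outcome plus log(days since PCI). Add ACS type, already on the form, for the cardiac endpoints. The baseline value belongs in the model because both aims concern improvement.
- **Early/late table:** if results are shown by time since PCI, label the table descriptive only.
- **Leave unchanged:** the entry window and the four strata. A two-level time factor would double the strata to 8 in a trial of 120, and covariate adjustment does the work without that.

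The cost is one form field, known for every patient at eligibility, and a few degrees of freedom. No extra patients, visits or measurements are needed. If enrolment has begun, the interval can be filled in from source records, and the model should be fixed before unblinding.
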